## **10. Sample size**

For the primary objective, we expect a sensitivity of 95%. We aim to include 73 patients for a maximum length of the 95% confidence interval equals 10% (+/-5%). Assuming a NSTEMI prevalence of 10%, 730 patients must be analyzed to achieve this precision. By anticipating a 10% rate of non-exploitable data (missing value, lost to follow-up, etc.), 800 inclusions are necessary.

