## **13. Level of statistical significance (p-values, confidence intervals, one- or two-sided)**

Statistical significances will be achieved for p-values lower the 5% by using two-sided alternative hypotheses and two-sided 95% confidence intervals. The 95%CI will be estimated by non-parametric bootstrap.

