## **21. Handling missing data**

We will perform complete case analyses. Excluded patients will be described against the others to evaluate a possible selection bias. The methodology described in the section 16 will be applied.

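### The 800 inclusions fall slightly short: at the SAP's own 10% loss they leave 720 patients and 72 NSTEMI, not the required 730 and 73

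*SAP*

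**What the plan says.** The sample size in SAP section 10 is built in three steps.

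1. With an expected sensitivity of 95%, 73 NSTEMI patients are needed for a 95% confidence interval of at most 10% in full length (±5%).
2. The case count is converted to a cohort size: "Assuming a NSTEMI prevalence of 10%, 730 patients must be analyzed to achieve this precision".
3. The cohort size is raised for losses: "By anticipating a 10% rate of non-exploitable data (missing value, lost to follow-up, etc.), 800 inclusions are necessary".

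Two other sections bear on the third step. Section 13 sets "two-sided 95% confidence intervals", which fixes the multiplier behind the first step. Section 21 states "We will perform complete case analyses", so a patient with non-exploitable data drops out of the analysed number.

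**The concern.** The first two steps set a minimum for the number analysed, and the third should give the number of inclusions that reaches it at the assumed loss rate. It does not: 800 is below the result of either usual way of allowing for a 10% loss. On the SAP's own assumptions, the study would end with fewer analysed patients and fewer expected cases than the same paragraph requires.

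What is at stake is mainly the accuracy of the justification. A sample size paragraph is normally carried into the study report, and there it would say that 800 inclusions deliver 730 analysable patients at 10% loss.

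**Working it through.** **Inputs**, all from SAP section 10 unless noted: sensitivity p = 0.95; half-width d = 0.05; prevalence 0.10; loss rate 0.10; stated inclusions 800; z = 1.96 (two-sided 95%, section 13).

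**Step 1: cases, reproducing the plan's figure.** The Wald precision formula is n = z² × p × (1 − p) / d².

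1.96² × 0.95 × 0.05 / 0.05² = 72.99, rounded up to **73**. This matches the SAP.

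**Step 2: analysed patients, reproducing the plan's figure.** 73 / 0.10 = **730**. This matches the SAP.

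**Step 3: inclusions.**

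| Method | Calculation | Result |
|---|---|---|
| 10% of inclusions are lost | 730 / (1 − 0.10) = 811.1 | 812 |
| 10% added to the analysed number | 730 × 1.10 | 803 |
| SAP | – | 800 |

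The first row is the correct one for a loss rate among those included. The second is a common shortcut. The stated 800 is 12 below the first and 3 below the second.

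**Step 4: what 800 inclusions deliver.**

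- Analysed at 10% loss: 800 × 0.90 = 720, which is 10 below 730.
- Expected NSTEMI: 720 × 0.10 = 72, which is 1 below 73.
- Highest loss rate that still leaves 730: 1 − 730/800 = 8.75%.

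**Step 5: effect on precision.** Full Wald length = 2 × 1.96 × √(0.95 × 0.05 / n).

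| NSTEMI cases | Half-width | Full length |
|---|---|---|
| 73 | 5.00% | 9.999% |
| 72 | 5.03% | 10.07% |

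There is no slack in step 1. The unrounded requirement is 72.99, so 73 is the smallest whole number that meets the 10% limit, and 72 just misses it.

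**The case against.** The case on the other side accepts the arithmetic and argues that the point is too small to raise.

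- **Rounding.** 800 looks like 803 rounded to a convenient target. It is within 0.4% of 803 and 1.5% of 812. This is plausible, but the SAP does not say so, and a number presented as the minimum needed is rounded up, not down.
- **Precision to the stated resolution.** The SAP gives the target in whole percentages, and 10.07% is 10% at that resolution. This is fair, and it shows how little precision is lost. It does not make 720 equal to 730.
- **Chance variation is larger.** With 720 analysed patients and 10% prevalence, the standard deviation of the NSTEMI count is √(720 × 0.1 × 0.9) = 8.05, so one expected case is about an eighth of it. The observed sensitivity matters more too: among 73 cases, 69 detected gives a Wald length of about 10.4% and 70 detected about 9.1%. This stands.
- **The reported interval is not Wald.** Section 13 specifies a non-parametric bootstrap. That is correct, so the 0.07-point difference describes the planning calculation and does not forecast the reported interval. The Wald formula is still the right one for checking section 10, because it reproduces the 73 exactly.
- **Replacement of patients.** A rule for replacing non-exploitable patients could be in the protocol, which is not at hand, so the SAP's silence on it is no defect. The point does not depend on it: section 10 itself derives the 800 from the 10% loss rate, and that derivation fails on its own figures.

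These arguments limit the size of the point. None of them makes the third step correct.

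**Conclusion.** The concern holds, as a minor error. At the loss rate the SAP assumes, 800 inclusions give 720 analysed patients and 72 expected NSTEMI, against the 730 and 73 it requires. The shortfall is 10 patients, one expected case and about 0.07 percentage points of planned interval length.

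This rests on the SAP's own values (95% sensitivity, 10% prevalence, 10% loss), on reading the loss rate as a share of inclusions, and on lost patients leaving the analysis, as complete-case analysis implies. Reading the 10% as an addition to 730 narrows the gap to 3 inclusions but does not close it. Uncertainty in the assumed prevalence matters far more to the final precision, and the primary objective is not threatened.

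**What to change.** Keep 800 inclusions and correct the sentence in section 10 in one of two ways:

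- say that 800 inclusions allow for up to 8.75% non-exploitable data while leaving 730 patients to analyse; or
- keep the 10% loss rate and say that it leaves 720 patients and about 72 expected NSTEMI, with an expected 95% confidence interval length of about 10.1%.

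Raising the target to 812 would also make the paragraph consistent, but the gain in precision is too small to call for it. The cost of either wording is one sentence in the SAP, with no extra patients and no change to any analysis.

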## **11. Interim analysis (timing, person, adjustment of the significance level)**

No interim analysis was planned.

## **12. Reporting the representativity of the studied population**

A flowchart will be decomposed according to the inclusion, non-inclusion criteria, and exclusions because of missing data for the disease diagnosis (NSTEMI, unstable angina, or major cardiac event at 30 days). The excluded patients will be compared to the others for identifying a potential selection bias.

## **13. Level of statistical significance (p-values, confidence intervals, one- or two-sided)**

Statistical significances will be achieved for p-values lower the 5% by using two-sided alternative hypotheses and two-sided 95% confidence intervals. The 95%CI will be estimated by non-parametric bootstrap.

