- To estimate its discriminative capacities by estimating the AUC and comparing its value with the one of the in-hospital HEART score estimated at 0h.
- To estimate its ability to rule-out the patients instead of the in-hospital evaluation at 0h for relieving emergency services, i.e., to achieve a negative predictive value equals to 99% (3) for at least 5% of the patients.
- To estimate its ability to rule-in the patients in the cardiology department instead of the in-hospital evaluation at 0h for reducing the time to treatment of the MI, i.e., to achieve a positive predictive value equals to 65.0% (Figure 1) for at least 10% of the patients.
- To evaluate its increase of capacities for discriminating patients with NSTEMI by considering additionally the venous troponin measured in hospital (difference in the AUC).

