## **19. Proposition and validation of a predictive tool for pre-hospital rule-out and rule-in**

The cohort will be divided into two parts: two thirds for learning and one third for validation. The description of the two samples will be performed with the same baseline variables listed in the section 16. No p-value will be computed because of the random allocation of the patients. Instead, standardized mean differences will be estimated to evaluate the comparability of the two samples.

From the learning sample, a logistic model will be estimated with LASSO penalization to select the subset of predictors among the following list of candidates: age, gender, body mass index, active smoking, stented heart disease, bypassed heart disease, compatible clinical history, delay after onset of pain lower than 3h; normal ECG evaluated by the HEMS, and the following risk factors: hypertension, diabetes, hypercholesterolemia, family history and hs-cTnI. The outcome will be the diagnosis of NSTEMI. We will perform a 20-fold deviance-based cross-validation to choose the best tuning parameter.

A particular attention will be paid to the interaction between hs-cTnI and the delay after onset of chest pain because the level of troponin may continue to grow up to three hours after the chest pain. This may lead to increase the proportion of false negatives.

From the validation sample, we will estimate its discriminative capacities by the ROC curve and the related AUC. Its goodness-of-fit will be evaluated by a calibration plot of the observed probabilities against the mean predicted probabilities for five subgroups of equal size. The corresponding Hosmer and Lemeshow statistic will be estimated.

Always from the validation sample, we will compute the in-hospital HEART score at 0h, the related ROC curve and AUC, and its difference with the pre-hospital predictive model.

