## **20. Investigation of the utility of the prediction model**

From the validation sample, we will estimate its ability to rule-out the patients instead of the hospitalization. For that purpose, we will estimate the percentage of event-free patients at hospital discharge (no NSTEMI) among the ones with a predicted probability of event less than 0.3. We will also estimate the percentage of patients with a predicted probability of event less than 0.3.

From the validation sample, we will estimate its ability to rule-in the patients instead of the in-hospital evaluation at 0h by the percentage of patient with the event (NSTEMI) among the ones with a predicted probability of event higher than 0.65. We will also estimate the percentage of patients with a predicted probability of event higher than 0.65.

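### The blanket bootstrap rule in SAP section 13 gives a zero-width or too-short 95% CI for the section 20 rule-out NPV if that NPV is near 99%: a minor, cheap improvement

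*SAP*

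**What the plan says.** SAP section 13 asks for "two-sided 95% confidence intervals" and fixes how they are obtained: "The 95%CI will be estimated by non-parametric bootstrap". It does not say which bootstrap form (percentile, basic, BCa) is meant, and it makes no exception for proportions close to 0 or 1.

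Section 20 works in the validation sample, which section 19 defines by the split "two thirds for learning and one third for validation". There, "we will estimate its ability to rule-out the patients instead of the hospitalization", measured as "the percentage of event-free patients at hospital discharge (no NSTEMI) among the ones with a predicted probability of event less than 0.3". This is an NPV at a fixed cut-off. Section 20 names no interval for it, so the general rule of section 13 applies.

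The related aim in section 7 is "to achieve a negative predictive value equals to 99% (3) for at least 5% of the patients". No exact or score interval, and no fallback for zero missed events, appears anywhere in the SAP.

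**The concern.** A non-parametric bootstrap can only reproduce values that were observed. If every validation patient below the cut-off is free of NSTEMI, every resample has an NPV of 100%, whatever the group size. The percentile and basic intervals have no width, a normal-approximation bootstrap has a standard error of zero, and BCa is undefined. With very few misses the percentile interval exists but is too short on its lower side.

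That lower side carries the information about how many NSTEMI might be missed. A report of 100% with a 95% CI of 100% to 100% would claim certainty that about 200 patients cannot supply. The SAP's own aim is an NPV of 99%, which is the region where the method does worst.

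**Working it through.** **Inputs from the SAP.** Section 10 expects a sensitivity of 95% with a CI of ±5 points: n = 1.96² × 0.95 × 0.05 / 0.05² = 72.99, so 73 cases. Dividing by the 10% prevalence gives 730, which reproduces "Assuming a NSTEMI prevalence of 10%, 730 patients must be analyzed to achieve this precision". The validation third is 730 / 3 ≈ 243 patients, with about 24.3 NSTEMI.

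**Zero misses.** The bootstrap gives 100% to 100%. The exact (Clopper-Pearson) lower limit is 0.025^(1/n): 98.1% for n = 197, 98.3% for n = 219, and 98.5% if all 243 are below the cut-off.

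**Group size (assumption; the SAP gives none).** Take 10% prevalence, a roughly calibrated model, and the section 7 rule-in aim met (PPV 65% in 10% of patients: 24.3 patients, 15.8 events). That leaves 24.3 − 15.8 = 8.5 events among 243 − 24.3 = 218.7 patients. Those still above 0.3 must have an event rate of at least 30%. At NPV 99% the smallest group below 0.3 therefore solves

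8.5 − 0.01n = 0.3 × (218.7 − n), so 0.29n = 57.11 and n ≈ 197.

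The upper end shown is 219. It is already extreme: 24.3 − 2.2 = 22.1 events among 24 patients above the cut-off, or 92%.

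**Coverage at a true NPV of 99%.** This is an exact binomial enumeration, with the bootstrap number of misses distributed as Bin(n, observed misses / n) and the fitted model and split held fixed.

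| n | zero misses, 0.99ⁿ (interval wholly above the truth) | upper limit below the truth | percentile coverage |
|---|---|---|---|
| 197 | 13.8% | 1.5% | 84.7% |
| 219 | 11.1% | 0.2% | 88.8% |

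Nearly all the error is optimistic, against a nominal 2.5% on each side. With one miss at n = 219, the 97.5th percentile of resampled misses is 3. The percentile lower limit is then 1 − 3/219 = 98.6%, against an exact limit of 97.5%. The basic form covers only 64.4% at n = 219, and with one miss it runs from 99.1% to 100.5%.

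**Comparators at NPV 99%.** Over this range of n, Clopper-Pearson fails only with six or more misses (probability 1.5% at n = 197, 2.4% at n = 219), so it covers 98.5% to 97.6%. Wilson covers 93.5% to 97.8%.

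**What NPV the 0.3 cut-off would give (assumption: calibrated, equal-variance binormal score, 10% prevalence).** Let d = √2 × Φ⁻¹(AUC). The cut-off is x = [ln((0.3/0.7) × (0.9/0.1)) + d²/2] / d. The missed share is 0.1 × Φ(x − d), and the correctly ruled-out share is 0.9 × Φ(x). For AUC 0.90: d = 1.812 and x = 1.651. The missed share is 0.1 × 0.436 = 0.0436, or about 11 of 243. The correctly ruled-out share is 0.9 × 0.951 = 0.856. NPV = 0.856 / (0.856 + 0.0436) ≈ 95.2%.

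| AUC | NPV | misses in 243 | chance of zero width | percentile coverage |
|---|---|---|---|---|
| 0.85 | 93.7% | about 14 | below 0.01% | about 95% |
| 0.90 | 95.2% | about 11 | 0.002% | 94.5% |
| 0.95 | 96.9% | about 7 | 0.1% | 94.7% |
| 0.97 | 97.7% | about 5 | 0.6% | 94.8% |
| 0.99 | 98.8% | 2 to 3 | 7% | 92.4% |

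Coverage is uneven because the data are discrete: 91.4% at AUC 0.93 and 88.7% at AUC 0.98.

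**The case against.** The strongest reply is that an NPV near 99% is unlikely at this cut-off. Section 20 does not link 0.3 to the 99% aim, and an ordinary good model would leave several NSTEMI below it. That stands, and it sets the size of the point: zero width becomes appreciable only with near-perfect discrimination.

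It is also true that section 20 promises a percentage and mentions no interval, that the bootstrap form is open, and that the share below 0.3 is reported as well, so a reader could recover the denominator and compute an exact limit. None of this makes the stated rule suitable. Anyone who adds an interval to this NPV is directed to the bootstrap, and every common form fails with zero misses.

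Three stronger readings are tempting, and the SAP supports none of them.

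- *Coverage collapses.* The section 7 minimum of 5% of patients is about 12 people, where percentile coverage at NPV 99% would be 11.4%. But with 10% prevalence and rough calibration, a 0.3 cut-off cannot leave so few below it. Even a group of 168 (coverage 80.8%, zero width 18.5%) needs an event rate of exactly 30% among everyone above the cut-off, which conflicts with the rule-in aim.
- *The rule-out conclusion would be wrong.* The SAP ties no decision to the lower limit, and the 99% in section 7 is not stated as a bound on it.
- *The bootstrap is wrong throughout.* Nothing here bears on AUCs, AUC differences, the ICC or Youden-threshold quantities. A PPV near 65% in 24 patients (10% of 243) has percentile coverage of 94.1%.

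**Conclusion.** The point holds in a limited form. The zero-width result with no misses is a matter of algebra and does not depend on group size. The under-coverage of about 85% to 89% depends on a true NPV at the 99% target and on the group sizes assumed above. At the NPV of about 94% to 98% that the binormal assumption gives for AUC 0.85 to 0.97, coverage is about 91% to 95% and the interval is close to adequate. What is at stake is a misleadingly certain interval on one secondary figure, not a planned conclusion. Confidence is high in the algebra and moderate in the practical size, because the SAP gives neither the expected NPV at the cut-off nor the size of the group. This is a minor improvement, worth making because it costs almost nothing.

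**What to change.** Add one sentence to SAP section 13: the section 20 rule-out NPV, at its fixed cut-off in the validation sample, gets a Clopper-Pearson 95% CI (Wilson is an acceptable alternative). Keep the bootstrap for AUCs, AUC differences, the ICC, the Youden threshold, and sensitivity and specificity at that threshold. Using the same exact or score interval for the section 20 PPV and for the shares ruled out and ruled in is optional and would serve consistency only.

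The change needs standard software and no new data, and it should be made before the validation results are seen. The price is a slightly wider, conservative interval with Clopper-Pearson. Wilson is less conservative but can fall to 93.5% coverage at NPV 99%.

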## 7. Objectives and related endpoints (units and calculations used to derive outcomes)

An adjudication committee oversees the validation of the events considered in the following objectives and outcomes.

The primary objective is to determine the thresholds of the pre-hospital capillary and venous hs-cTnI that maximizes the Youden J index. The event to predict is the non ST-elevation acute coronary syndrome at hospital discharge (NSTEMI). The sensitivity is the proportion of patients with an hs-cTnI level higher or equal to the threshold among the patients with the syndrome. The specificity is the proportion of patients with an hs-cTnI level lower than the threshold among the patients without the syndrome. We will also determine the ROC (receiver operating characteristic) curves and the related areas under the curve (AUC) related to the two methods.

**Figure 1.** Decision tree for ruling-out ruling-in the patients with a suspicious myocardial infarction after their emergency admission.

The secondary objectives of the VALIDATE project are to study the discriminative capacities of the pre-hospital hs-cTnI measured by two different testing methods (capillary and venous whole blood), and to select the method with the best performances. For that purpose, we aim:

- To evaluate the most relevant hs-cTnI measurement between the capillary- and the venous-based methods by i) reporting the concordance between the pre-hospital hs-cTnI measured by the capillary and venous methods, and ii) comparing the related AUCs for discriminating patients with NSTEMI.
- To estimate and compare the discriminative performances of the two methods by considering the Major Adverse Cardiac Events (MACE) occurrence at 30 days (ROC curves, AUCs, and Youden J index). Note that a NSTEMI systematically implies an outcome of MACE at 30 days.

Depending on the results at this stage, the rest of the analyses will be performed according to the venous or the capillary method, depending on their discriminative performances. In case of an equivalence, we will choose the capillary method because of its feasibility in a real-life setting. We will further investigate its usefulness to improve the ruling-in and ruling-out process described in Figure 1. More precisely, we aim:

- To propose a pre-hospital predictive tool of the probability of NSTEMI at hospital discharge. The candidate predictors will be the available demographic, clinical data, and pre-hospital hs-cTnI level.

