## 18. Description of the hs-cTnI discriminative capacities

The primary objective is to determine the pre-hospital capillary hs-cTnI threshold that maximizes the Youden index. The Euclidean distance (also called the upper-left index) will also be estimated. For the corresponding thresholds, the results will be reported on the related ROC curve. The related effectives (true positives and negatives, false positives and negatives) will be reported. The accuracy will also be computed (proportion of true results). On the same figure, the results related to the pre-hospital venous-based hs-cTnI will be reported. The difference between the two curves will be estimated and the corresponding bilateral test to evaluate the significance will be performed from the 95%CI (confidence interval).

The intra-class correlation coefficient (ICC) will additionally provide a single measure of the agreement between the capillary- and venous-based methods. Two scatter plots will be proposed to represent the degree of concordance: a plot with the pre-hospital venous-based hs-cTnI (y-axis) against the capillary-based measurements (x-axis), and a Bland–Altman plot with the difference between the two measurements (y-axis) against the average of the two measurements (x-axis).

The discriminative performance of the pre-hospital hs-cTnI will then be estimated for the MACE at 30 days as outcome. For that purpose, two ROC curves on the same graph will be plotted for the capillary- and venous-based measurements. The related AUCs and differences will be reported.

Depending on the results at this stage, the rest of the analyses will be performed according to the venous or the capillary method. In case of an equivalence, we will choose the capillary method because of its feasibility in a real-life setting.

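### Section 13's plain bootstrap intervals for Youden J and sensitivity at the data-chosen cut-off ignore the selection; with a binormal marker and 73 cases they cover below 95%, mostly erring optimistically

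*SAP*

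**What the plan says.** - **SAP section 13** asks for "two-sided 95% confidence intervals" and adds: "The 95%CI will be estimated by non-parametric bootstrap". It does not say which bootstrap interval is meant (percentile, basic or bias-corrected), whether the cut-off is chosen again in each resample, or whether optimism is corrected.
- **SAP section 7** sets the primary objective: to "determine the thresholds of the pre-hospital capillary and venous hs-cTnI that maximizes the Youden J index". **Section 18** restates it for capillary blood: "The primary objective is to determine the pre-hospital capillary hs-cTnI threshold that maximizes the Youden index". It then reports the true and false positives and negatives at that threshold.
- **SAP section 10** sizes the study on the precision of sensitivity: "we expect a sensitivity of 95" per cent, and "We aim to include 73 patients for a maximum length of the 95% confidence interval equals 10% (+/-5" percentage points). The total follows: "Assuming a NSTEMI prevalence of 10%, 730 patients must be analyzed to achieve this precision".
- **SAP section 19** plans a learning and a validation sample, but only for the LASSO tool. The primary cut-off has no such separation.

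**The concern.** The cut-off is picked because it looks best in these patients, and its J and sensitivity are then read from the same patients. Both are therefore optimistic on average. An interval with honest 95% coverage has to allow for that choice, and neither natural reading of section 13 does so:

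- **Cut-off chosen again in each resample, percentile limits.** The maximum in a resample tends to exceed the maximum in the sample, which itself tends to exceed the truth. The interval is pushed upward twice.
- **Cut-off held fixed in the resamples.** The interval treats a selected cut-off as if it had been known beforehand.

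The error bars on the primary result would then claim more confidence than they have. For a marker intended to help rule out NSTEMI, a lower limit for sensitivity that is too high is the unhelpful direction.

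**Working it through.** **1. The plan's own figure.** Section 10 treats sensitivity as a simple proportion at a known cut-off:

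n = 1.96² × 0.95 × 0.05 / 0.05² = 72.99, so 73 cases; 73 / 0.10 = 730 analysed, hence 730 − 73 = 657 non-cases.

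For 10% unusable data, 730 / 0.90 = 811 or 730 × 1.10 = 803; the stated 800 is close to both. The figure reproduces, but it makes no allowance for choosing the cut-off.

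**2. Direction.** Let Ĵ(c) be the observed J at cut-off c, and ĉ the cut-off that maximises it. Then E[Ĵ(ĉ)] ≥ max J(c) ≥ J(ĉ): the observed maximum overstates the best attainable J on average, and overstates the J of the published cut-off by more. The first inequality applies again from sample to resample.

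**3. Size, by simulation.** Assumed, because the SAP gives no distribution: non-cases N(0, 1), cases N(μ, σ²) on a log-type scale, AUC 0.75-0.99, equal and unequal SDs, 73 cases and 657 non-cases. The main run used 1000 trials with 600 resamples per scenario; a check run used 500 with 400. Monte Carlo error at 80% coverage is 1.96 × √(0.8 × 0.2 / 1000) = 2.5 points in the main run and up to about 4 in the check run.

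Check of the model at AUC 0.95, σ = 1: μ = 2.326, since 2.326/√2 = 1.645 and Φ(1.645) = 0.95. The best cut-off is μ/2 = 1.163, giving sensitivity Φ(1.163) = 0.878 and J = 2 × 0.878 − 1 = 0.755 (unrounded values).

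Coverage (%) in the check run:

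| Scenario | Maximal J, percentile | J at selected cut-off, percentile | Sensitivity at selected cut-off, percentile | Same, cut-off fixed | J, optimism-shifted | Sensitivity, optimism-shifted |
|---|---|---|---|---|---|---|
| AUC 0.95, continuous | 79.0 | 71.0 | 78.8 | 81.2 | 88.4 | 88.4 |
| AUC 0.90, rounded to 0.06 SD | 84.4 | 79.0 | 86.4 | 86.2 | 91.6 | 91.8 |
| AUC 0.90, rounded to 0.10 SD | 85.0 | 79.4 | 88.6 | 88.8 | 92.0 | 91.6 |
| AUC 0.85, case SD 2, rounded to 0.06 | 85.8 | 82.8 | 89.6 | 91.2 | 93.6 | 94.8 |
| μ = 1.3, case SD 0.55, rounded to 0.06 | 80.6 | 73.8 | 83.0 | 82.8 | 89.4 | 87.6 |

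In these five scenarios the percentile interval for J at the selected cut-off lay wholly above the truth in 17.0-29.0% of trials and wholly below in 0-0.2%. For the maximal J at AUC 0.90 in the main run, the misses were 19.4% above and 0.1% below, against a nominal 2.5% each way. Mean optimism at the selected cut-off was 0.02-0.05 for both J and sensitivity.

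**4. At the SAP's own sensitivity of 95%** (specificity 95% assumed), the percentile interval covers the maximal J 76%, J at the selected cut-off 68%, and sensitivity there 72% (78% with the cut-off fixed). A cut-off fixed in advance already gives only 88%. So about 95 − 88 = 7 points of the sensitivity shortfall are small-sample discreteness, and 88 − 78 = 10 to 88 − 72 = 16 points come from selection.

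**5. Other variants.** Basic and bias-corrected intervals cover the maximal J about 83-92% of the time; bias-corrected intervals cover sensitivity at the selected cut-off 79-95%. With coarse rounding (0.25 SD), percentile coverage is 87-92% for J and 91% for sensitivity.

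**The case against.** Four points on the other side have weight.

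- **The plan is underspecified, so no single coverage can be attached to it.** This stands. A reader might infer that the trial's intervals will have some definite coverage such as 70%. The SAP names no interval type, re-selection rule or marker distribution, so every figure here is conditional on assumptions. What does not depend on one variant is that both readings, cut-off chosen again or held fixed, undercover in the scenarios simulated.
- **A reader might infer that the bootstrap is invalid in principle for a maximised J.** That goes too far. With a smooth marker and a single optimum the problem is finite-sample bias. At ten times the sample size (AUC 0.90, 150 trials), basic and bias-corrected coverage of the maximal J was 93%, percentile 89%, and coverage of sensitivity at the selected cut-off 95%. The difficulty arises at 73 cases.
- **The target matters.** For sensitivity at the true optimal cut-off, the re-selecting percentile interval covers 86-97%. But that cut-off is unknown; the one readers will use is the one published.
- **Section 18 does not itself name an interval for J or sensitivity.** True, and the primary objective is literally the threshold. The intervals follow from section 13's general rule and from section 10, which sizes the study on an interval for sensitivity. Coverage for the threshold itself was not assessed, and nothing is claimed about it here.

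**Conclusion.** The point holds in this form: as written, section 13 gives intervals for J and for sensitivity at the data-chosen cut-off that do not allow for the choice. With a binormal marker, 73 cases and 657 non-cases, the percentile interval covers about 75-85% for the maximal J, 68-84% for J at the selected cut-off and 72-90% for sensitivity there. With the cut-off held fixed, the figures are about 80-87% for J and 78-89% for sensitivity. Single scenarios fall a few points outside these ranges, depending on rounding and Monte Carlo error. Misses for J are almost all on the favourable side. Basic and bias-corrected intervals narrow the gap but mostly stay below 95%.

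The point concerns the intervals. It does not show that the threshold is wrong, that the data or design are unusable, or that selection explains the whole shortfall in sensitivity. It should be corrected before the analysis, because the stated confidence of the primary result depends on it.

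**What to change.** Amend section 13 as follows.

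1. Exempt J, sensitivity and specificity at the data-chosen cut-off from the plain bootstrap rule, and state that the target is performance at the published cut-off.
2. Name one of these two methods in advance:
   - **Repeated 10-fold cross-fitting.** Choose the cut-off in nine folds, classify the tenth, and repeat over several random splits. Average the cross-fitted proportions over repeats. Form Wilson limits (l, u) for sensitivity (n = number of cases) and specificity (n = number of non-cases). Combine them for J by MOVER: lower = J − √[(Se − l₁)² + (Sp − l₂)²], upper = J + √[(u₁ − Se)² + (u₂ − Sp)²].
   - **Optimism-shifted bootstrap.** Take the percentile interval with the cut-off held fixed. Subtract from both limits the mean, over resamples, of performance at the resample's own cut-off in the resample minus performance at that same cut-off in the original data.
3. Report the true and false positive and negative counts at the single chosen cut-off alongside, labelled as apparent. Under cross-fitting they will not match the corrected estimates exactly, and the text should say so.
4. Keep the bootstrap for AUCs and AUC differences.

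**What it achieves.** Coverage is about 91-94% for J and 87-93% for sensitivity with cross-fitting, and about 88-94% and 86-95% with the optimism shift. Neither is exactly nominal, and the SAP should not claim that it is.

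**What it costs.** Wording and a few lines of code, with no new data. With cross-fitting, J intervals are about 10-35% longer than percentile ones (at AUC 0.95, mean length 0.164 against 0.135, and 0.164/0.135 = 1.21). The estimate is slightly less favourable, and the remaining misses for sensitivity lean to the pessimistic side.
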